33 implementation outcomes. The quantitative evaluation (1) monitors each programme's care
34 process through quality indicators, (2) a multiple-time point survey study to compare programme
35 participants' pre- and post- outcomes on patient engagement (collaboRATE and 13-item Patient
36 Activation Measure; PAM), healthcare experiences (Consumer Assessment of Healthcare
37 Providers and System Clinician and Group Survey Version 3.0; CG-CAHPS), health status and
38 quality of life (Barthel Index of Activities of Daily Living, fall counts, the EuroQol questionnaire
39 and the Control, Autonomy, Self-realisation and Pleasure scale; CASP-19), impact on caregivers
40 (Zarit Burden Interview) and societal costs (Client Service Receipt Inventory). (3) A

41 retrospective cohort design to assess healthcare and cost utilisation between participants of the
42 programme and a propensity score matched comparator group.

43 **Discussion:** The GSH sites share a common goal to increase the accessibility of essential
44 services to frail older adults and provide comprehensive care. The results of this evaluation study
45 will provide valuable evidence to the impact and effectiveness of the GSH and inform the design
46 of similar programmes targeting frail older adults.

47

48 Trial Registration: To be provided

49

50 Keywords: Frailty care, comprehensive geriatric assessment, care coordination, multidisciplinary
51 team care

52

53 List of Abbreviations used in manuscript:

54

UK	United Kingdom
CGAs	Comprehensive Geriatric Assessments
GSH	Geriatric Services Hub
RHS	Regional Healthcare Systems
CFS	Clinical Frailty Scale
GPs	General Practitioners
NTFGH	Ng Teng Fong General Hospital
PAM-13	13-item Patient Activation Measure
CG-CAHPS	Consumer Assessment of Healthcare Providers and System Clinician & Group Survey Version 3.0
ADL	Activities of Daily Living
CASP-19	19-item Quality of Life Scale
ZBI	Zarit Burden Interview
CSRI	Client Service Receipt Inventory
NRIC	National Registration Identity Card
GLM	Generalised Linear Models
IRRs	Incident-rate Ratios

55

56 **Background**

57 Frailty denotes a state of increased vulnerability due to age-associated decline in function
58 and reserve such that the ability to cope with day-to-day or acute stressors is compromised (1). As
59 a result, frail older adults are usually more susceptible to adverse outcomes including disability,

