To assess the process of development and implementation of the new programme	
• To examine the perceptions, roles, responsibilities, and experience in developing and implementing each programme• To understand the workflow from the perspective of each profession for each of the new programmes• To improve competency of primary care providers in identifying, caring and managing geriatric patients in the community• To explore differences in contextual factors across the five sites that have influenced implementation experiences and outcomes• To understand care recipients' experiences in receiving frailty care in the community	Qualitative - Semi-structured in-depth interview with key policy and programme decision-makers Qualitative - Semi-structured focus group discussions with health and social care professionals and care recipients Qualitative – Participant observations Quantitative – Longitudinal monitoring of process indicators
To assess the health, quality of life, and user experience effects on care recipients and the burden of care on primary caregivers	
• To compare outcomes between baseline, 3- and 6-months for each programme	Quantitative - Pre-test post-test design using survey-based data collection
To determine the impact on healthcare utilisation and cost impact of the new programme	
• To assess the use of healthcare services and costs between participants and non-participants for each programme	Quantitative - Retrospective cohort design with propensity score matched comparators

208
209 Based on the components the sites are funded for (Table 1), we will evaluate the GSH
210 program conducted by Ng Teng Fong General Hospital (NTFGH) based on evaluation objective 1
211 – to assess the process of development and implementation of the new programme. The focus is
212 on competency building, with the funding being utilised to cover the time spent by trainers and
213 trainees. In addition, the funding will not be used to cover healthcare costs incurred by patients.

214 Based on these considerations, evaluation objectives 2 and 3 would not be representative of the
215 results of the program. The remaining four sites will be evaluated on all three evaluation objectives
216 as their funding structures includes subsidising the healthcare costs of patients.

217 **Qualitative Evaluation**

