246 desired outcomes. We will monitor quantitative process outcomes longitudinally on a quarterly
247 basis over the three-year pilot timeframe to assess the level of receptivity towards the new
248 programme, partner organisations' ability to accurately screen for frailty, provision of personalised
249 and goal-oriented care, and care-continuity.

250 Second, a single cohort, pre-test post-test design (pre-experimental design) will be used to
251 quantify the impact of participation in the programme on care recipient-reported health outcomes,
252 experience of care, and caregiver's burden. There will be no randomised parallel control group
253 due to programmes' reluctance, as they expect high refusal rates from patients. In addition, the
254 new model encompasses different care components tailored to each patient's needs, which renders
255 it impractical to conduct a 'true' experimental design with randomisation and a separate control
256 group (44).

257 Third, a retrospective pre-post, matched-groups design will be implemented to compare
258 healthcare utilisation and cost. Due to the absence of a parallel control group, we have opted for a

259 quasi-experimental design to determine the cost impact of introducing the new programme within
260 the current healthcare landscape.

261 **Study Sample**

262 Qualitative Evaluation

263 For semi-structured in-depth interviews, at least two participants representing each of the
264 five implementation sites and the Ministry of Health will be purposefully sampled. They will
265 include decision-makers who are higher-level administrators or clinicians who have the authority
266 to make policy and implementation decisions. It will also include individuals who are familiar with
267 the hospital's overall frailty strategy, and those who led the development and implementation of
268 the programme.

269 We will conduct a series of focus group discussions where multiple stakeholders are
270 identified through purposive sampling. First, we will conduct focus group discussions with
271 members of the core implementation team at each of the five sites— defined as individuals with
272 time funded through the programme who have been providing services in the GSH for at least six
273 months. They may include doctors, nurses, allied health professionals, and administrative or
274 operations personnel. Second, for each site, at least five members of the staff from partner

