275 organisations including primary care clinics, and aged care facilities will be identified for another
276 round of focus group discussions. They may include the heads of doctors, nurses and
277 administrative staff who provided services within the new programme for at least six months.
278 Third, we aim to identify at least ten participants who receive care under the new model for at least
279 three months for the last round of focus group discussions. They must be able to take part in
280 conversation for at least 60 minutes. For individuals who do not have the capacity to participate,
281 his/her primary caregiver is eligible for participation.

282 We will conduct participant observations to better understand the processes involved by
283 shadowing 3 to 5 members of the staff over the course of one week per site to account for day-to-
284 day variations and job role differences.

285 Quantitative Evaluation

286 First, quality indicators will be developed to measure the processes of care for all individuals
287 enrolled into each programme. The relevant sub-populations accessing each care component will
288 form the denominator for computation of the indicators.

289 Second, we aim to recruit patients enrolled in the new programme. A target sample of 300
290 participants per site will be recruited. The sample was calculated based on the Barthel Index (100
291 points) – a scale to assess physical functioning, the key health outcome expected to improve as a
292 result of participation in the GSH. We computed the sample size for each participating site using
293 the dependent t-test to detect a small effect size of 0.2 (based on $\beta = .80$, $\alpha = .05$) (45). The result
294 was a minimum sample size of 156 per participating site. Allowing 20% rejection rate at the first
295 instance and a subsequent attrition rate of 30%, we would need to approach 300 individuals at the
296 first instance.

297 (Insert) Figure 1 Study sample for quantitative evaluation

298 Third, propensity score matching will be used to match programme enrollees and a
299 constructed comparator group. Both groups will be matched based on their probability of being
300 enrolled into the programme conditional on baseline covariates (46). The propensity score can be
301 used to mitigate selection bias in a non-randomised study. All programme enrollees will be
302 included as cases. Data on comparators will be derived from a Ministry of Health dataset

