- 354 1. GSH sites offer a range of medical, social and other services through either direct provision
355 or referrals. Given that the model is intended to bridge service gaps (conduct of CGA in
356 the community), in the short-term, we hypothesis **an increase in the utilisation of**
357 **appropriate services** (rehabilitation, ambulatory services) in this time-limited programme.
- 358 2. GSH participants are expected to benefit from the comprehensive package of health and
359 social services and multidisciplinary team approach. With **better care coordination and**
360 **improved access**, it is likely to elicit a **higher level of satisfaction** relative to comparator
361 groups.
- 362 3. Education of the client about self-care and making decisions about potential care options
363 with inputs from a multidisciplinary team is expected to result in **higher level of shared**
364 **decision making** and **engagement** relative to comparator groups.
- 365 4. It is hypothesised to result in **better functional status and health outcomes**, **might reduce**
366 **the healthcare utilisation** (emergency hospitalisation, nursing home admission),
367 **caregiver burden** and **the associated indirect cost**. In turn, we might expect **overall costs**
368 **to be lower** compared to the comparison group.

369 An interviewer-administered survey will be conducted to collect data on demographic and

370 baseline health status, and data measuring the impact of the programme on patient activation, user

371 experience and satisfaction with care, health status, quality of life, the burden of care on primary

372 caregivers, and health utilisation and cost. The data are collected at baseline, 3-months and 6-

373 months (Table 5). After obtaining informed consent, participants will be asked to complete a

374 survey estimated to take about 45 to 90 minutes. Participants will complete the survey up to three

375 time-points – baseline (within 1 month of programme enrollment) and at 3-months and 6-months.
376 The primary caregiver will also be asked to complete a 5 to 10-minute survey at the same three
377 time points on caregiver burden. In the event a participant is clinically certified to have dementia,
378 we will allow a proxy respondent to answer on behalf of the main participant. Participants will
379 receive a token of appreciation for their involvement in the study.

380 Table 5. List of indicators for measuring programme impacts

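### Hypotheses 2 and 3 promise a contrast with comparators, but their outcomes are surveyed only in enrollees, so only pre-post change can be reported

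*Combined protocol and SAP*

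**What the plan says.** Study Procedure (Quantitative Evaluation) lists four hypotheses. Hypothesis 2 expects more satisfaction, and hypothesis 3 more shared decision making and engagement, each "relative to comparator groups". Table 5 assigns experience of care to CG-CAHPS and places collaboRATE and PAM-13 under patient engagement. All three belong to the interviewer survey at baseline, 3 months and 6 months.

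The survey is described in four places:
- Abstract, Methods: it compares participants' "pre- and post- outcomes on patient engagement (collaboRATE and 13-item Patient" Activation Measure).
- Table 2, objective 2: "To compare outcomes between baseline, 3- and 6-months for each programme".
- Evaluation Design, Quantitative Evaluation: "Second, a single cohort, pre-test post-test design (pre-experimental design) will be used to" measure impact on reported health outcomes, experience of care and caregiver burden.
- Study Sample, Quantitative Evaluation: "Second, we aim to recruit patients enrolled in the new programme", with the sample size taken from a dependent t-test.

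The comparators are described separately:
- Abstract, Methods: a "retrospective cohort design to assess healthcare and cost utilisation between participants of the" programme and matched comparators.
- Evaluation Design: "Third, a retrospective pre-post, matched-groups design will be implemented to compare" healthcare utilisation and cost.
- Study Sample: comparator data come from a Ministry of Health dataset on the health status of older adults in the community.

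On scope, Evaluation Design says: "The remaining four sites will be evaluated on all three evaluation objectives".

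**The concern.** A hypothesis stated against comparators needs the same outcome measured in both groups. Here the outcome is measured in one group only. If the wording stays, the only result available for hypotheses 2 and 3 is a change among enrollees. Such a change mixes any programme effect with background change over time and regression to the mean. A reader who takes the hypotheses at face value would read that change as a controlled finding. Later analysis cannot repair this, because the comparator responses will not exist.

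**Working it through.** **1. Outcome by outcome.**

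| Hypothesis | Outcome | Instrument (Table 5) | Enrollees | Comparators |
|---|---|---|---|---|
| 2 | Satisfaction / experience | CG-CAHPS | Baseline, 3, 6 months | None described |
| 3 | Shared decision making | collaboRATE | Baseline, 3, 6 months | None described |
| 3 | Engagement | collaboRATE, PAM-13 | Baseline, 3, 6 months | None described |

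Counts: 2 of 4 hypotheses, 0 of 3 instruments with comparator measurement, and 4 of 5 sites assessed on objective 2 (Ng Teng Fong is assessed on objective 1 only).

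**2. Does the survey sample size contain a second arm?** The inputs in Study Sample are a dependent t-test, effect size 0.2, alpha 0.05, and 0.80 (written as beta, read here as power). Sidedness is not stated. For a paired t-test, power is the probability that a noncentral t with n − 1 degrees of freedom and noncentrality 0.2√n exceeds its critical value.
- One-sided: the smallest n is 156 (power 0.800). This reproduces the plan's figure exactly.
- Two-sided: n = 199, which does not match.
- Inflation: 156 / (0.8 × 0.7) = 278.6, or 279. The plan's 300 lies above this.

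The 156 is a within-person number with no comparator arm. Its one-sided basis is a separate matter and not part of this point.

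**3. Could the linked dataset supply comparator responses?** Study Procedure says the dataset built for the enrollee-comparator analysis will also hold everything collected in the survey. That survey is given to consenting programme participants and their caregivers. Comparator data come from records already held by the Ministry. Merging adds enrollees' answers to the file and creates none for comparators. The stated purpose of the merge is utilisation and cost.

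**4. Could the comparators be other sites?** Table 2 sets its comparisons within each programme, and no between-site test of these outcomes is planned.

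**5. What would keeping the wording require?** The documents give no SD or expected difference for these instruments. Assume a between-group difference of 0.2 SD, alpha 0.05 and power 0.80, before refusal and attrition.
- 1:1, two-sided: 2 × (1.960 + 0.842)² / 0.2² gives 393 per group. One-sided: 310 per group.
- Two comparators per case: 295 cases and 589 comparators two-sided, or 232 and 464 one-sided.
- If 300 are approached per site, 300 × 0.8 × 0.7 = 168 complete. Two groups of 168 would have power Φ(0.2 × √(168/2) − 1.960) = Φ(−0.127), about 45% two-sided.

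These figures are illustrative. The inconsistency does not depend on them.

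**The case against.** The strongest reply is that the plan is clear about what will be done. Abstract, Table 2, design and sample agree, and only two trailing phrases in the hypotheses depart from them. Evaluation Design says openly that there is no randomised concurrent control, gives reasons, and labels the survey pre-experimental. The sample is sized on the Barthel Index, not on these three instruments. The first limitation also says that data collection covers only people who accept the programme. No planned estimate or sample changes under the fix.

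Most of this stands, and it sets the severity. A reader might infer that the plan hides the lack of a control; it does not. What remains is that the hypotheses contradict the disclosed design. The design section offers a quasi-experimental remedy for utilisation and cost only. Neither of the two listed limitations says that survey outcomes lack a comparator: one concerns people who seek care elsewhere, the other unmeasured confounding after matching.

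Two pieces of text that look like further support should not be used. The analysis section's allowance for within-subject correlation would be needed with or without comparators. The strengths paragraph on attributed outcomes concerns health outcomes and cost, not these instruments.

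Figure 1, the quantitative study sample, is not shown. It would have to contradict all four descriptions of the survey to rescue the wording.

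**Conclusion.** Hypotheses 2 and 3 are wrong as written: the planned data cannot support a contrast with comparators on satisfaction, shared decision making or engagement. Severity: should fix. The conclusion rests on the text and assumes that Figure 1 adds no comparator survey.

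Three stronger readings are tempting and not supported:
- That the pre-post result will overstate the programme's benefit. The documents give nothing from which the size or direction of bias could be computed.
- That the single-cohort survey is itself an error. It is a disclosed choice with stated reasons; the fault is in hypotheses that claim more than it can give.
- That hypothesis 4's cost clause cannot be tested. It is hedged, and it can be tested for public system cost (primary, specialist, emergency and inpatient care) in the matched cohort. Only its reach is unclear, because the CSRI's social and informal care costs have no described comparator data.

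**What to change.** 1. Replace hypotheses 2 and 3 with a statement of this kind: *Among enrollees, satisfaction (CG-CAHPS), shared decision making (collaboRATE) and patient engagement (collaboRATE, PAM-13) will be higher at follow-up (3 and 6 months) than at baseline.*
2. Report these outcomes as pre-post change, not as an effect against comparators.
3. Add to Strengths and limitations: *Survey outcomes have no comparator, so background change cannot be separated from programme effect.*

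Cost: the wording of two hypotheses and one added sentence, with no new data and no change to the sample. The downside is narrower claims on experience and engagement. Keeping the between-group wording would instead mean surveying comparators with the same three instruments, which no text plans.

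Optional and separate: state in hypothesis 4 that the comparison with the matched group covers public healthcare system cost, and that CSRI social and informal care cost is reported for enrollees only.

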138 community volunteers are screening for frailty amongst older adults. Community nurses have also
139 started to perform rapid and targeted geriatric and frailty assessments at neighbour-based nursing
140 posts (31). However, the link between frailty assessments and the wider network of community
141 care providers needs to be strengthened. To address this gap, the Singapore Ministry of Health
142 provided funding to test the effectiveness of a new programme for frail adults aged 65 years old
143 and older – the GSH –, which will be piloted by five sites. While there is no national consensus on
144 the tools for identifying or grading frailty, the Ministry has specified the use of the Clinical Frailty
145 Scale (CFS) (32) to support the enrollment of older adults living with mild, moderate or severe

146 frailty into the GSH programme. This study protocol will focus on the evaluation of these five
147 pilot sites. Due to geographical locations, the five pilot sites fall under the jurisdiction of two
148 different RHS in Singapore. Each site focuses on its existing strengths and resources to ride on or
149 build new partners within their RHS to provide community-anchored referral-gated geriatric care.
150 Through these partnerships, the GSH functions as a network of providers led by a core team of
151 acute hospital-based healthcare professionals (33). Each site acts as a consolidation point in the
152 community by actively receiving referrals from various services providers. All GSH sites share
153 the following goals:

- 154 • To provide early identification of frailty and offering comprehensive and coordinated care
155 in the community through collaborative working arrangements with partners, including
156 polyclinics, general practitioners (GPs), and community health and social service providers
- 157 • To provide CGAs to identify needs of frail older adults and to establish a care plan for each
158 individual patient
- 159 • To increase frail older adults access to essential services and transit across shared primary
160 care and other community-based providers more seamlessly
- 161 • To provide core services of geriatric assessments, nursing support, therapy service and case
162 management/care coordination
- 163 • To build capabilities by providing training to the primary care staff in identifying, caring
164 and managing frail older adults.

165 Despite these common goals, each GSH was designed differently to best harness their

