342 **Quantitative Evaluation**

343 Quantitative process indicators will be developed based on the logic model within inputs
344 from each of the five implementing sites to ensure agreement that they accurately describe the key
345 processes, which can be observed and described to support the achievement of desired outcomes.
346 Indicators are computed for each month and at quarterly intervals for each GSH site. Table 4
347 outlines the full list of requested process indicators.

348 Table 4. List and description of process indicators

Indicators	Measure	Definition	Data collection time-points
Patient recruitment			
Number of patients recruited by GSH sites	Receptivity towards GSH	No. of enrollees recruited into each GSH site after being referred	Monthly
Number, proportion of referred patients who fall within CFS 5-7	Accurate identification of frailty	CFS profiles of patients referred as scored by referral sources	Monthly
Patient-focused care management			
Number, proportion of CGA completed	Personalised care	No. of CGA completed vis-à-vis no. of assessments initiated	Monthly
Number, proportion of ICP developed	Personalised, goal-oriented care	Total no. of ICP developed vis-à-vis the no. of CGA completed	Monthly
Coordination of care			
Number of multidisciplinary rounds/discussions	Team-based care	No. of multidisciplinary team discussions conducted	Monthly
Number, proportion of referrals to services	Efficiency in care continuity	No. of referrals made to different services and the share of each service to the total no. of referrals	Monthly
Number, proportion of actualised referrals	Care continuity	No. of actualised first referrals at respective services vis-à-vis the no. of referrals made to each service	Monthly
Appointment waiting time to first appointment	Efficiency in care continuity	Waiting time for a first appointment to a referred service	Monthly
Competency building			
Number of community-based staff trained to conduct specific activities (CGA, exercise)	Competency building	No. of community-based healthcare participants in training sessions organised by the GSH ¹	Quarterly

349 Legend: CFS = Clinical Frailty Score; CGA = Comprehensive Geriatric Assessments; ICP = Individualised Care
350 Plans; GSH = Geriatric Service Hub

351 ¹Training sessions include preceptorship-based training and case discussions

352

353 The evaluation aims to assess the impact of GSH. We hypothesised that

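### The pre-test survey may be taken up to a month after enrolment with nothing placing it before the first assessment or service, so the pre-post change may be diluted.

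*Combined protocol and SAP*

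**What the plan says.** The Quantitative Evaluation part of Evaluation Design describes the survey component: "Second, a single cohort, pre-test post-test design (pre-experimental design) will be used to" "quantify the impact of participation in the programme on care recipient-reported health outcomes", along with experience of care and caregiver burden. It states that there is no randomised parallel control group. Table 2 gives the contrast: "To compare outcomes between baseline, 3- and 6-months for each programme".

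Study Sample says who is surveyed: "Second, we aim to recruit patients enrolled in the new programme. A target sample of 300" per site. The survey therefore follows enrolment. Study Procedure sets the time points as "baseline (within 1 month of programme enrollment) and at 3-months and 6-months".

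The section on Geriatric Services Hubs lists assessment and care planning among the goals shared by all sites: "To provide CGAs to identify needs of frail older adults and to establish a care plan for each" patient. The third hypothesis in Study Procedure names a mechanism that could act from the first contacts: "Education of the client about self-care and making decisions about potential care options", which is expected to raise shared decision making and engagement.

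The Data Analysis section gives only generalised linear models that allow for within-subject correlation. It does not mention care received before the baseline survey, and neither does Strengths and limitations. No section says when the CGA or services begin relative to enrolment, or whether 3 and 6 months are counted from enrolment or from the baseline survey.

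**The concern.** With no control group, the within-person change from baseline is the only effect estimate for the survey outcomes. Any benefit already present when the baseline survey is taken is subtracted from that estimate.

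The problem is sharpest for collaboRATE, CG-CAHPS and PAM-13. The first two ask about experience of care and of providers. A participant surveyed after the CGA may already be rating the programme's own care, so that the pre and post scores could both describe the programme. Activation could move early through the education that the protocol expects to raise engagement. The Barthel Index measures physical function and is less likely to shift within a month.

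If the dates of survey and first service are not captured, a small or null change cannot be told apart from a baseline that already contained programme care. The planned effect is small (0.2), so little dilution can be absorbed.

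**Working it through.** **Inputs from the protocol (Study Sample).** Paired t-test, standardised effect d = 0.2, power 0.80 (printed as beta), alpha 0.05 with sidedness not stated, minimum 156 per site, 20% refusal, 30% attrition, 300 approached.

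**Step 1: reproduce the stated 156.** Exact power comes from the noncentral t distribution with n − 1 degrees of freedom and noncentrality d√n.
- One-sided alpha 0.05: the smallest n with power of at least 0.80 is 156, an exact match. The normal approximation ((1.645 + 0.842)/0.2)² gives 155.
- Two-sided alpha 0.05: n = 199, which does not match.

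The figures below use the one-sided basis because it reproduces the plan. Which sidedness is intended is a separate question.

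**Step 2: dilution.** Let f be the share of the benefit already present at the baseline survey. The detectable effect becomes 0.2(1 − f). The documents give no value for f, so every row after the first is an assumption.

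| f | Effect | Power at 156 | n needed for 80% |
|---|---|---|---|
| 0 | 0.200 | 80.0% | 156 |
| 10% | 0.180 | 72.4% | 193 |
| 1/6 | 0.167 | 66.6% | 224 |
| 1/3 | 0.133 | 50.5% | 350 |

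Approaching 300 implies 300 × 0.8 × 0.7 = 168 completers. The corresponding powers are 82.6%, 75.1%, 69.4% and 53.0%.

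The values 1/6 and 1/3 correspond to one month out of six and one month out of three. They assume linear accrual from enrolment, every baseline a full month late, and follow-up counted from enrolment. Each row applies d = 0.2 to one visit taken alone. Under linear accrual the 3-month effect is half the 6-month effect, so the last two rows cannot both describe one trial.

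**Step 3: what the unstated anchor does.** Take a 30-day delay, with visits at 91 and 182 days.
- *Linear accrual, visits counted from enrolment:* loss 30/91 = 33% at 3 months and 30/182 = 16% at 6 months.
- *Linear accrual, visits counted from the baseline survey:* day 30 to day 121 spans the same 91 days, so the loss is 0%. The same holds at 6 months.
- *Front-loaded accrual, assumed 60-day half-life, B(t) = 1 − 2^(−t/60):* B(30) = 0.293, B(91) = 0.650, B(182) = 0.878. Counted from enrolment, the loss is 0.293/0.650 = 45% at 3 months and 0.293/0.878 = 33% at 6 months. Counted from the survey, it is 1 − (B(121) − B(30))/B(91) = 29%, and 29% again at 6 months.

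So the anchor alone can move the loss from one third to nothing at 3 months under linear accrual. The range of 0 to one third in Step 2 is illustrative and not a bound.

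**The case against.** The strongest reply is that exposure before baseline is not documented. The protocol sets an outer limit of one month; it does not say that surveys will be late or that care starts at once. Table 4 tracks "Waiting time for a first appointment to a referred service" as a process indicator, so referred services may well begin after a wait. The outcome used for sizing, the Barthel Index, is the one least likely to move in a month. All of this stands, and it is why the point is worded as a possibility.

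It also stands that the plausible loss is smaller than the worst case, because not every baseline will fall on day 30, and that the linear loss disappears if visits run from the baseline survey.

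A reader might infer more than the documents support in three ways:
- *That the effect is certainly biased towards no change.* Dilution acts in that direction, but an uncontrolled change is also open to regression to the mean and natural decline, so the net direction is not settled.
- *That differing survey delays distort site comparisons.* Table 2 specifies contrasts over time for each programme, and Data Analysis prespecifies no between-site contrast of survey outcomes.
- *That the main analysis should use only participants with a pre-service baseline.* That would select on survey speed and on the wait for services, which may be related to need, and it could take a site below 156.

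The objection does not remove the gap itself. Nothing in the plan prevents a post-service baseline, records one or examines its effect.

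**Conclusion.** The concern holds as a possible dilution that the plan neither prevents nor would detect. It rests on three documented facts: the survey comparison is uncontrolled, participants are already enrolled when recruited to it, and baseline may fall up to a month after enrolment without having to precede the CGA, care plan or first service.

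The size depends on when services start, how quickly they act, how late surveys are and what the follow-up visits are counted from. The documents give none of these beyond the one-month limit. The power range of 80% to about 51% is therefore a sensitivity range under assumed losses of 0 to one third, not an estimate. It is calculated for the generic planned effect of 0.2. The concern is most credible for shared decision making, care experience and activation. A firm statement that the Barthel comparison will lose power would go beyond what the protocol shows.

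**What to change.** In Study Procedure:
- State that the baseline survey should be completed before the CGA or first programme service where feasible. This concerns survey scheduling only; care need not wait for the survey.
- Record the dates of enrolment, CGA, first service and each survey.
- State whether the 3- and 6-month surveys run from enrolment or from the baseline survey.

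In Data Analysis:
- Keep all participants in the main pre-post contrast.
- Prespecify a sensitivity analysis, either restricted to participants with a pre-service baseline or adjusted for days from first service to baseline survey.

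The cost is a few date fields, one extra analysis and somewhat tighter scheduling of the first survey. The dates should be captured as they occur, since they may not be recoverable reliably later.
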